STATISTICAL POWER OF THE STUDY

The primary endpoint of the study is the proportion (%) of episode-free days in the TBS group, compared with the SA, after a 48-week intervention period. To ensure a 80% power to detect a 15% difference (corresponding to 1 day per week) in episode-free days between the treatment groups, at least 64 children per group were required, assuming a standard deviation of 27% for symptom-free days seen in a previous study [Bisgaard et al. 2006], and a possible drop-out percent of 20%. The calculation is based to reject the primary hypothesis with 5% significancy level.

STATISTICAL ANALYSIS PLAN

Normality of the distribution of continuous variables are to be evaluated by Shapiro-Wilk test. The overall difference between the treatment groups is to be evaluated by using either analysis of variance, Kruskal-Wallis, log-rank, chi-squared, or Fisher's exact tests. Pairwise analyses are to be performed by using Mann-Whitney U, chi-squared, or Fisher's exact tests. Bonferroni correction is to be applied in pairwise analyses by multiplying each P-value by 3. Influence of confounding factors on the primary outcome is to be assessed by conducting the two-way factorial analysis of variance. $P<0.05$ is to be considered statistically significant. All study participants are to be included in safety analyses, and those with diary data available are to be included in primary analysis. All analyses are to be performed as intention-to-treat. IBM SPSS Statistics (version 22.0; Armonk, NY, US) is to be used for all analyses.

RESEARCH METHODS AND MATERIAL, ETHICAL ISSUES

Inclusion criteria:

1. Children at the age of 6 to 35 months.
2. Two to four physician-confirmed episodes of wheeze and/or shortness of breath.
3. Parents/legal representatives with sufficient written and spoken skills in Finnish language

Exclusion criteria:

1. Birth before 36th week of gestation.
2. Suspected/diagnosed chronic parenchymal lung disease or a structural airway defect, or a history of thoracotomy with pulmonary resection.
3. A history of congenital or acquired heart disease, including any unstable or life-threatening cardiac arrhythmia.
4. Constipation with a need of regular medication, or a diagnosed/suspected structural defect in the gastrointestinal tract.
5. A history of malignancy, or other significant chronic disorder, disease, or defect.

Study population and study design

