195 consecutive patients will be recruited in the study. Before enrolment, respiratory infections should be treated, and significant thoracic anomalies should be excluded by taking a chest X-ray scan. Background information is questioned as follows: gestational stature, birth weight and length, ethnic background, allergy to food and inhaled allergens diagnosed or strongly suspected by a physician, respiratory symptoms, wheezing episodes confirmed by a physician, other significant illnesses or diagnoses, operations, medication, atopic diseases in family members, smoking and pets at home, moist or mould problems at home.

The study children will be randomized into three groups. One third of the patients (SA group, n=65) will receive inhaled salbutamol (Ventoline Evohaler® 0.1 mg/dose), i.e. rescue medication, to be used 0.2 mg 4 to 6 times a day as needed for wheeze and shortness of breath via a plastic spacer, Babyhaler®, during the whole study (i.e. SA group). One third of the patients (FPS group, n=65) will be randomized to receive fluticasone propionate (Flixotide Evohaler® 125 µg/dose), to be given 125 µg twice a day via Babyhaler®, beginning at the onset of an upper respiratory tract infection and continuing for 7 to 14 days as needed, and in addition, inhaled salbutamol (Ventoline Evohaler® 0.1 mg/dose), i.e. rescue medication, to be used 0.2 mg 4 to 6 times a day as needed for wheeze and shortness of breath via Babyhaler®, during the whole study. One third of the patients (TBS group, n=65) will be randomized to receive tiotropium bromide (Spiriva Respimat® 2.5 µg/dose), to be given 5 µg once a day via AeroChamber Plus®, beginning at the onset of an upper respiratory tract infection and continuing for 7 to 14 days as needed, and in addition, inhaled salbutamol (Ventoline Evohaler® 0.1 mg/dose), i.e. rescue medication, to be used 0.2 mg 4 to 6 times a day as needed for wheeze and shortness of breath via AeroChamber Plus®, during the whole study. The intervention will last for 48 weeks. The drugs and the plastic spacers will be supplied by the pharmacy of Helsinki University Hospital.

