The parents are taught to keep diary on wheeze and shortness of breath, and on the use of rescue and intervention medication. The use of medications is controlled by measuring weights of the inhalators at the end of the 48-week intervention. After the 48-week intervention period, medication for episodes of wheeze and shortness of breath will be planned individually and the patients are remitted back.

Control phone calls by a research nurse will take place at 4, and 8 weeks from the beginning of the intervention. The control visits will take place at 12, 24, 36, and 48 weeks from the beginning of the intervention. In all cases, the first (week 0) and last (week 48) visits are to be organized at HUH Skin and Allergy Hospital. For those subjects living in Helsinki, the control visits at 12, 24, and 36 weeks will take place at HUH Skin and Allergy Hospital, and for those living in surrounding municipalities of Helsinki, the control visits (at 12, 24, and 36 weeks) will take place at a local hospital (Jorvi, Porvoo, or Hyvinkää), i.e. nearest hospital of the living place of the study subject.

Adverse events requiring unscheduled medical attendances, as well as serious adverse events requiring hospital admission are to be charted. In case the study patient is diagnosed a chronic illness needing regular controls and physician care, the investigator will evaluate the situation and considers, case by case, a withdrawal of the patient from the study. However, hospitalization for wheezing or shortness of breath, or administration of drugs other than the interventional ones are not considered as indications for the discontinuation of the study, as these occasions are regarded as normal occurrences in early childhood wheezing illnesses. Per oral or inhalant corticosteroids may be used in any of the study groups as additional medications if they meet the criteria stated in the Finnish Current Care Guidelines for asthma in children [see <http://www.kaypahoito.fi/web/english/home>].

In case of the discontinuation, wheezing episodes of the study children will be treated according to the Finnish Current Care Guidelines for asthma in children [see <http://www.kaypahoito.fi/web/english/home>].

Blood and urine samples

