A venous blood sample is a part of the routine diagnostic evaluation and is drawn from all children (5-15 ml of blood, <1% of the circulating blood volume) during the first visit, and at the 48-week visit. In addition, a urine sample is collected during the first visit, and at the 48-week visit. Following parameters are to be analysed: total blood cell count, serum allergen-specific immunoglobulin E concentrations for a mixture of inhalant and food allergens (Phadiatop combi®). In addition, serum 1-2 ml and urine 10 ml are taken for storage for analysis of immunological markers in future.

Handling of data

Detailed personal information on the study patients is collected by interviewing the caregivers during the study visits and by phone calls by study investigators and registered study nurses, and by collecting data from patient files in medical records. No data enabling identification of the patient is included in the case report forms or electronic files including the study data. IBM SPSS version 22.0 is used for electronic handling of the study data, including saving and analysing study material in an electronic form. The case report forms are saved in lockers in locked storage rooms. Only certain named investigators, a study monitor, and study nurses have access to the case report forms and the electronic study data. Whenever any changes are performed in the case report forms, the changes are to be verified by a signature. In case the changes are made in electronic data, a new file is to be created to document changes in the data.

Discontinuation of the study leads to the intention-to-treat analysis of the collected case-specific data.

The study files and data are preserved until the study children reach school age, in order to give an opportunity for a final evaluation of the study patients' respiratory state. However, such long-term evaluations reaching school age are out of the scope of the present research protocol.

Insurances

Injuries related to the actions of investigating physicians or nurses, or injuries related to the study investigations or measurements are to be covered with a patient insurance.

Pharmaceutical injuries insurance covers possible unexpected study drug-related adverse events.

Ethical considerations

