To date, repeated episodes of wheezing or other persistent troublesome lung symptoms are treated only with short-acting beta-2-agonists unless there are multiple physician-confirmed episodes and risk factors present [Finnish Current Care Guidelines for Lower respiratory tract

infections in children and for Asthma; <http://www.kaypahoito.fi/web/english/home>]. In the study protocol, an earlier start of an intermittent controller therapy for those randomized to TBS or FPS groups, as well as intensive follow-up of symptoms for all intervention groups can be seen as advantages of the study.

Possible unexpected drug-related adverse events can be seen as possible disadvantages of the study; however, occurrence of drug-related adverse events is attempted to be minimized by including conditions that may increase the risk for drug-related adverse events in the exclusion criteria.

Approval of the study protocol is to be asked from the National Committee on Medical Research Ethics (TUKIJA), and written informed consent is to be obtained from each patient's legal representative prior to randomization. The trial is to be conducted in accordance with the guiding principles of the Declaration of Helsinki, and in accordance with the International Conference on Harmonisation Good Clinical Practice guidelines and local regulations.

Any substantial amendments in the study protocol are to be announced in a written form (Substantial Amendment Notification Form) both to the Finnish Medicines Agency (Fimea) and to TUKIJA. In addition, any changes among study personnel (i.e. investigators) and/or study sites are to be announced to Fimea and TUKIJA.

IMPLEMENTATION: TIMETABLE, BUDGET, DISTRIBUTION OF WORK

Timetable

Recruitment of patients was started in April 2016. Based on the number of referrals of patients with wheezing episodes or other persistent troublesome lung symptoms to the hospital district of Helsinki and Uusimaa, it is estimated that the last patient will be recruited in the study at the end of year 2019. The last follow-up visit will be timed at the end of year 2020. Thereafter, all the study data will be saved in an electronic form, analysed, and published in international forums.

Budget

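### The 15 ml upper end of the blood draw is not under 1% of blood volume for nearly all children at entry, on assumed weights and blood volumes per kg

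*Combined protocol and SAP*

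**What the plan says.** The section Blood and urine samples states: "A venous blood sample is a part of the routine diagnostic evaluation and is drawn from all children". It gives the amount as "5-15 ml of blood, <1% of the circulating blood volume" and places the draws at the first visit and at the 48-week visit. The listed uses are a blood count and an IgE test on an allergen mixture. The section then adds: "In addition, serum 1-2 ml and urine 10 ml are taken for storage for analysis of immunological markers in future". It does not say whether the blood for that serum lies inside the 5-15 ml.

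The Inclusion criteria admit "Children at the age of 6 to 35 months". The available text gives no body weight at either draw, no blood volume per kg, and no explicit rule linking the volume drawn to the child's size.

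**The concern.** One parenthesis gives a volume range and a share of blood volume for the same draw in the same children. The share is the only statement in the section of how large the draw is relative to the child, so the ethics committee and the staff taking the sample rely on it. If the two figures cannot both hold at the upper end, the text overstates how much blood may be taken within the limit. A person drawing blood from a 10 kg child then has two permissions that disagree: up to 15 ml by volume, or a good deal less by share. What is at stake is the accuracy of a stated participant-burden figure for a procedure done twice in every child.

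**Working it through.** **Inputs from the documents.** Draw of 5 to 15 ml; share under 1%; all children; two draws (week 0 and week 48); age 6 to 35 months at entry. Forty-eight weeks is about 11 months, so age at the second draw is about 17 to 46 months.

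**Assumptions, not in the documents.** Blood volume of 70-90 ml/kg, and the body weights used below.

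**Formulas.**
- Share = draw / (weight × ml per kg).
- Smallest weight at which a draw equals 1% = draw / (0.01 × ml per kg).
- Volume equal to 1% = 0.01 × weight × ml per kg.

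**Step 1: try to reproduce the stated share at each end of the range.**
- 5 ml: 5 / 0.01 = 500 ml of blood; 500/90 = 5.6 kg and 500/70 = 7.1 kg. The stated share is broadly reproduced.
- 15 ml: 15 / 0.01 = 1,500 ml of blood, a step that needs no assumption; 1,500/90 = 16.7 kg, 1,500/80 = 18.75 kg and 1,500/70 = 21.4 kg. The stated share is reproduced only in a heavy child.

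**Step 2: results by weight.** Ranges run over 70-90 ml/kg.

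| Weight | Volume equal to 1% | 5 ml as share | 15 ml as share |
|---|---|---|---|
| 7 kg | 4.9-6.3 ml | 0.79-1.02% | 2.38-3.06% |
| 10 kg | 7.0-9.0 ml | 0.56-0.71% | 1.67-2.14% |
| 12 kg | 8.4-10.8 ml | 0.46-0.60% | 1.39-1.79% |
| 14 kg | 9.8-12.6 ml | 0.40-0.51% | 1.19-1.53% |
| 16 kg | 11.2-14.4 ml | 0.35-0.45% | 1.04-1.34% |
| 18 kg | 12.6-16.2 ml | 0.31-0.40% | 0.93-1.19% |

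**Step 3: how far off would the blood-volume assumption have to be?** For 15 ml to equal 1%, the child would need 1,500/10 = 150 ml/kg at 10 kg, 1,500/14 = 107 ml/kg at 14 kg, or 1,500/16 = 93.8 ml/kg at 16 kg. All three lie above the assumed range.

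**Step 4: how many children?** This step also assumes normally distributed weights with means of 7.7 kg at 6 months, 9.7 at 12, 10.9 at 17, 12.3 at 24, 14.2 at 35 and 16.0 at 46, standard deviations of 0.9 to 2.0 kg, and ages spread evenly. It gives the share of children in whom a 15 ml draw would exceed 1%. It does not estimate how many will actually give 15 ml.

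| | 70 ml/kg | 80 ml/kg | 90 ml/kg |
|---|---|---|---|
| Entry, all ages | about 100% | 99.97% | 99.2% |
| Week 48, all ages | 99.97% | 98.8% | 91.3% |
| Week 48, oldest (46 months) | 99.7% | 91.5% | 63.1% |

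**The case against.** The best defence is that the parenthesis sets two limits to be met together: the volume varies with the child, and "<1% of the circulating blood volume" is the ceiling. That is a fair reading. On it the stricter limit governs, so no small child need give more than 1%. What it does not rescue is the quoted maximum. With 1% as the ceiling, 15 ml is out of reach for nearly every child at entry. Even at 16 kg it is 15/14.4 = 1.04 to 15/11.2 = 1.34 times the volume that fits.

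Three further points stand and limit the finding. The lower end of the range is broadly right. The mismatch is less universal at week 48: at 90 ml/kg, over a third of the oldest children would meet the limit even with 15 ml. And the text describes the sample as part of routine evaluation, although it also takes serum for later research.

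A reader might infer that the plan takes around 3% of blood volume from small infants. The documents do not support that. The figure pairs the largest draw with the smallest child, and nothing says a small infant gives 15 ml. The listed tests do not show a need for it either.

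**Conclusion.** Wrong as written, and minor. The upper volume and the stated share do not fit together for nearly all children at entry and for most at week 48. At 10 kg the largest draw would be about 1.7-2.1% of blood volume, and at 14 kg about 1.2-1.5%. The 1,500 ml threshold is plain arithmetic. Its translation into weights rests on an assumed 70-90 ml/kg, and the proportions of children rest also on assumed weights by age. The conclusion at entry holds across that whole range; at week 48 it weakens toward 90 ml/kg.

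It would go too far to conclude that the section lacks any protective limit, since the 1% can be read as one, or that children have been harmed. The documents show no harm, and the two draws are 48 weeks apart. The endpoint, sample size and analysis are unaffected.

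**What to change.** In Blood and urine samples, state the 1% as the binding limit and replace the fixed range with a maximum per draw tied to the child's weight on the day. The maximum should cover all blood taken, including that for stored serum. One workable cap is below about 0.7 ml/kg: 0.7/90 = 0.78% and 0.7/70 = 1.0%, so it keeps the draw under 1% across the assumed range. If the sponsor prefers another blood volume per kg, the text should state it and set the cap at 1% of it. There should be no fixed 5 ml minimum, and stored serum should be reduced first in the smallest children. Keeping the range and quoting a larger percentage instead is not advised, because that would remove the only protective limit in the section.

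The cost is small:
- One sentence changes, with an amendment notice to the medicines agency and the ethics committee if the sponsor judges it substantial.
- A weight is needed at each draw. The background list in Study population and study design names only a birth weight ("gestational stature, birth weight and length, ethnic background"), though current weight may be recorded elsewhere. Weighing should be easy to arrange, because "the first (week 0) and last (week 48) visits are to be organized at HUH Skin and Allergy Hospital".
- The smallest infants give slightly less serum for storage. At 0.7 ml/kg a child under 5/0.7 = 7.1 kg gives less than 5 ml; at 6.5 kg the maximum is 0.7 × 6.5 = 4.55 ml.

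The Timetable notes that "Recruitment of patients was started in April 2016", so the correction reaches only draws not yet taken.

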The preliminary results of the tiotropium trial including asthmatic children from age of 1 year on (trial number: NCT01634113) [Vrijlandt et al. 2018], showed no differences in safety profiles between those receiving tiotropium 5 µg, those receiving tiotropium 2.5 ug, and those receiving placebo. No serious adverse events occurred in either of the tiotropium groups during the 12-week intervention period, whereas 3 of the 34 children receiving placebo experienced a serious adverse event (i.e. appendicitis, bronchopneumonia and exacerbation of asthma, viral upper respiratory infection), requiring hospital admission. Among other adverse events, there were no undesirable anticholinergic effects, or no differences in occurrence of adverse events between the intervention groups [Vrijlandt et al. 2018].

In addition, an earlier clinical trial on a short-acting non-selective anticholinergic agent, ipratropium bromide, in 25 children aged 5 to 15 years with severe acute asthma, found no significant differences in side effects between the study groups [Reisman et al. 1988]. Moreover, there is a recent report on tiotropium in cystic fibrosis, including 24 children aged 5 to 11 years, and 24 patients aged 12 years or older [Konstan et al. 2014]. Only two of these patients with cystic fibrosis experienced a serious adverse event, neither of which was considered drug-related [Konstan et al. 2014].

OBJECTIVE

The primary AIM of the study is

- 1) to find out the effect of intermittent tiotropium bromide and salbutamol as needed (TBS) versus intermittent fluticasone propionate and salbutamol as needed (FPS), or solely, salbutamol as needed (SA) on episode-free days in infants and toddlers with recurrent episodes of wheeze and/or shortness of breath.

Episode-free days are defined as those days during which there are no symptoms of wheeze and/or shortness of breath, no unscheduled medical visits for wheeze and/or shortness of breath, and no use of rescue or supplementary controller medications [Guilbert et al. 2006].

The secondary AIMS of the study are

to find out the effect of TBS versus FPS or SA treatment on

- 1) number of unscheduled physician visits for episodes of wheeze and/or shortness of breath,
- 2) need for bronchodilative medication,
and to evaluate
- 3) the safety of TBS versus FPS or SA treatment by paying attention to possible adverse events during treatment

in infants and toddlers with recurrent episodes of wheeze and/or shortness of breath.

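### The plan does not commit to counting unscheduled wheeze visits to week 48 after a child discontinues, and its tests do not adjust for unequal time at risk

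*Combined protocol and SAP*

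**What the plan says.** - **Outcome.** The OBJECTIVE section gives as secondary aim 1 the "number of unscheduled physician visits for episodes of wheeze and/or shortness of breath". The intervention lasts 48 weeks.
- **After discontinuation.** The only rule on outcome data is in Handling of data: "Discontinuation of the study leads to the intention-to-treat analysis of the collected case-specific data". The Study population and study design section says how wheezing is then treated, but not whether outcome data are still gathered.
- **Sources.** Handling of data lists interviews with caregivers at visits, phone calls, and information obtained "by collecting data from patient files in medical records". The parent diary, as described, covers symptoms and medication. Physician visits are not listed among its contents.
- **Analysis.** The STATISTICAL ANALYSIS PLAN states: "All analyses are to be performed as intention-to-treat". For the primary analysis it adds that "those with diary data available are to be included in primary analysis". On tests: "Pairwise analyses are to be performed by using Mann-Whitney U, chi-squared, or Fisher's exact tests". Analysis of variance, Kruskal-Wallis and log-rank are also listed for overall comparisons. No rate model, offset or missing-data method is given for a count.
- **Expected loss.** The sample-size section allows for "a possible drop-out percent of 20", with no split by arm.

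**The concern.** A raw count of visits is comparable between arms only if the children were observed for the same time, or if the analysis allows for the difference. Intention-to-treat settles who is analysed and in which arm. It does not settle which data are obtained after a child leaves. Kruskal-Wallis and Mann-Whitney tests treat a child seen for 12 weeks with one visit the same as a child seen for 48 weeks with one visit. Log-rank handles time to an event, not a number of events.

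If counting stops when a child leaves, the arm that loses more children shows fewer visits and looks better than it is. This can hide a benefit of tiotropium or fluticasone if salbutamol-only families leave more often, or create an apparent benefit if an active arm loses more. Arm-related exit is plausible. No placebo is described, regimens and spacers differ between groups, and Ethical considerations presents earlier controller therapy as an advantage for the two active groups.

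**Working it through.** **Inputs from the documents:** 195 children, 65 per arm; 48 weeks; 20% drop-out; 15-point difference, SD 27, 80% power, 5% level (taken as two-sided).

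**Assumed, because the documents give no figure:** a true mean of 2.0 visits per child in every arm (4 also used in the simulation), drop-out by arm, and time of exit.

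**1. The plan's own figure.** n = 2 × [27 × (1.960 + 0.842) / 15]² = 50.9, so 51 per group. 51 / (1 − 0.20) = 63.75, so 64. The stated 64 per group reproduces. It concerns the primary endpoint; no calculation is given for visits.

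**2. Information at stake.** Drop-outs: 0.20 × 65 = 13 per arm, 39 in all. Full follow-up: 195 × 48 = 9,360 child-weeks. With uniform exits each drop-out loses 24 weeks on average: 39 × 24 = 936 child-weeks, or 10%.

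**3. Effect on recorded means.** With drop-out d and mean exit time f as a share of 48 weeks, the observed share of follow-up is 1 − d × (1 − f). If leavers are of average risk, recorded mean = 2.0 × that share. Halfway exit is f = 0.5; exit around week 12 is f = 0.25. The true ratio is 1.00 throughout.

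| Assumed drop-out, A v B | Recorded means, halfway exit | Ratio B/A, halfway | Ratio B/A, week 12 |
|---|---|---|---|
| 20% v 20% | 1.80 v 1.80 | 1.00 | 1.00 |
| 15% v 25% | 1.85 v 1.75 | 0.95 | 0.92 |
| 10% v 30% | 1.90 v 1.70 | 0.89 | 0.84 |
| 5% v 35% | 1.95 v 1.65 | 0.85 | 0.77 |

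Example: 0.75 × 2 + 0.25 × 1 = 1.75 and 0.85 × 2 + 0.15 × 1 = 1.85.

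**4. Effect on the test.** One pairwise Mann-Whitney test was simulated at nominal 5%, before the planned multiplication of P-values by 3. Settings: 65 per arm, gamma-Poisson counts (gamma shape 1), uniform exits, 4,000 runs per scenario, no true difference.

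| Assumed drop-out | Type I error, mean 2 | Type I error, mean 4 |
|---|---|---|
| 20% v 20% | 5.4% | 4.4% |
| 10% v 30% | 9.3% | 9.0% |
| 5% v 35% | 13.6% | 16.0% |

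**5. Is an offset enough?** For average-risk leavers, yes: 1.75 / 0.875 = 2.00 and 1.85 / 0.925 = 2.00. For leavers whose risk differs, no. Suppose they have twice the visit rate (4.0 v 2.0) and leave halfway, at 25% v 15%. True means are 0.75 × 2 + 0.25 × 4 = 2.5 and 0.85 × 2 + 0.15 × 4 = 2.3, a ratio of 1.09. Visits per unit of observed time are 2.0 / 0.875 = 2.29 and 2.0 / 0.925 = 2.16, a ratio of 1.06. Obtaining the later visits is therefore the main remedy, and the offset a supplement.

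**The case against.** Several points on the other side stand.

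- A reader might infer that the plan counts visits only up to discontinuation. It does not say so. It speaks of collected data, sets no cut-off, and is compatible with files being read later. What is missing is a commitment.
- A reader might infer that records could supply visits for all 195 children. That depends on continued permission and on records from every place of care being reachable. The available text settles neither. Records are also named for detailed personal information in general, not for visit counts.
- A reader might say that visits have no analysis set. The general intention-to-treat sentence covers them, and the diary restriction attaches only to the primary analysis.
- Visits are not separate from the primary endpoint: an episode-free day requires that no unscheduled visit took place. Nor are they free of parental influence, since parents decide when to seek care.
- Hospital admission for wheeze and use of other drugs "are not considered as indications for the discontinuation of the study", and added corticosteroids are allowed in any group under guideline criteria. This weakens the case that worsening salbutamol-only children will leave, but does not prevent a family from choosing to go.
- The example in step 5 could be read as proof that truncation erases a real difference, because both arms record 2.0 visits. That equality is built in: twice the rate over half the time gives 2.0 for any drop-out split. It shows the limit of an offset, not the likely size of bias.
- The plan's single 20% rate, applied equally to average-risk leavers, produces no false difference.

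**Conclusion.** The gap is real and worth closing, but it concerns a secondary outcome with no power calculation. The plan neither commits to ascertaining visits to week 48 after discontinuation nor says how unequal follow-up enters the comparison. If counting stops at exit, about 10% of child-weeks are lost at 20% drop-out with uniform exits. Bias needs drop-out, or the risk of those leaving, to differ by arm, and the documents do not show that it will. Under assumed average-risk leavers and halfway exit, a 10-point difference in drop-out shifts the ratio of means by about 5%, and a 20-point difference by about 11%. In the latter case, with uniform exits, type I error is about 9% instead of 5% before the Bonferroni step. The documents do not support a claim that the counts will in fact be truncated, or that they will be truncated against a particular arm.

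**What to change.** State in the SAP that:

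1. Unscheduled visits and admissions for wheeze or shortness of breath are taken from patient records, with dates, from randomisation to week 48. This applies to every randomised child whose family has not withdrawn permission for record access, whether or not study drug, diary or study visits have stopped.
2. These events are analysed by randomised arm.
3. The date to which records were followed is kept for each child. Because some children's records may not be available to week 48, a rate analysis (for example negative binomial with log time at risk as offset) is added as a sensitivity analysis.

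The cost is record review for roughly 39 children by existing staff, a few SAP sentences, and a check that the consent covers record access after a child stops. Visits made outside reachable records may still be missed, and the documents do not establish that this would be equal across arms. The sample size stays at 64 per group, with 195 recruited.
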